### **13.7.2 Medical Monitor**

The NIDA medical monitor, [name], will be available for making recommendations to the SI on the severity of any SAEs, the relatedness to the study drug, and for determining if the SAE should be reported to the FDA in a 7- or 15-day expedited report or an annual report (**Appendix I**). The medical monitor will also be responsible for tracking and assessing trends in the adverse events reported.

### **13.7.3 Clinical Monitors**

All SIs will allow representatives of the Sponsor to periodically review, at mutually convenient times during and after the study, all eCRFs and corresponding source documents for each subject. These monitoring visits provide the Sponsor with the opportunity to evaluate the progress of the study and to inform the Sponsor of potential problems at the study sites. The monitors will: ensure that submitted data are accurate and are in agreement with source documentation; verify that study drugs are properly stored and accounted for, verify that subjects' consent for study participation has been properly obtained and documented, confirm that subjects entered into the study meet inclusion and exclusion criteria, and assure that all essential documentation required by GCP guidelines are appropriately filed.

Clinical monitors will conduct a site initiation visit prior to the start of the study. At this visit, they will assure that proper study-related documentation exists, assist in training SIs and other site personnel in study procedures and GCP guidelines, confirm receipt of study supplies, and assure that acceptable facilities are available to conduct the study.

Routine monitoring visits by the Sponsor's representatives will be scheduled at appropriate intervals. At these visits, the monitors will verify that study procedures are being conducted according to the protocol guidelines. At the end of the study, they will advise on storage of study records and return of unused study drugs. All sites should anticipate visits by NIDA, the Sponsor, and the FDA.

### 13.8 Study or Site Discontinuation

The Sponsor has the right to terminate this study at any time. Reasons for terminating the study may include, but are not limited to, the following:

- The incidence or severity of AEs in this or other studies indicates a potential health hazard to subjects.
- Subject enrollment is unsatisfactory.
- Data recording is inaccurate or incomplete.

The Sponsor will continue those subjects currently in treatment to completion, if there is no significant safety issue.

### 13.9 Retention of Records

Study documentation includes all eCRFs, workbooks, source documents, monitoring logs, appointment schedules, sponsor and SI correspondence, and regulatory documents (*e.g.*, signed protocol and amendments, IRB correspondence, approved consent form and signed informed consent forms, Statement of Investigator form, and clinical supplies receipt and distribution records).

Source documents include all recordings of observations or notations of clinical activities and all reports and records necessary for the evaluation and reconstruction of the clinical research study. Accordingly, source documents include, but are not limited to, laboratory reports, ECG tracings, X-rays, radiologist reports, subject diaries, biopsy reports, ultrasound photographs, subject progress notes, hospital charts or pharmacy records and any other similar reports or records of any procedure performed in accordance with the protocol. Whenever possible, the original recording of an observation should be retained as the source document; however, a photocopy is acceptable provided that it is a clear, legible, and exact duplication of the original document. Clinical records for all subjects studied including history and physical findings, laboratory data, and results of consultations are to be maintained by the SI in a secure storage facility.

Government agency regulations and directives require that the SI must retain all study documentation pertaining to the conduct of a clinical trial. These documents must be kept for a minimum of two years after discontinuation of the IND or two years after the approval of a new drug application (NDA) and finalization of all marketing strategies. In all instances you must get permission from NIDA prior to disposition of any study documentation and materials.

### 13.10 Adverse Events Reporting

In accordance with FDA reporting requirements, all AEs occurring during the course of the clinical trial will be collected, documented, and reported by the SI or sub-investigator according to the specific instructions detailed in this section of the protocol and **Appendix I**. The occurrence of AEs will be assessed at each study visit beginning on the day the Informed Consent is signed through the Follow-up Visit at Week 16.

An AE is defined as any reaction, side effect, or untoward event that occurs during the course of the clinical trial, whether or not the event is considered investigational product-related or clinically significant. For this study, AEs will include events reported by the subject, as well as

clinically significant abnormal findings on physical examination or laboratory evaluation. A new illness, symptom, sign or clinically significant clinical laboratory abnormality or worsening of a pre-existing condition or abnormality is considered an AE. Stable chronic conditions, such as arthritis, which are present prior to clinical trial entry and do not worsen are not considered AEs. All AEs must be recorded on the AE CRF. The AE CRF is also used to record follow-up information for unresolved events reported on previous visits.

Each week, a study physician must review all new AEs reported the previous week and any events that were reported as continuing. All AEs, including clinically significant abnormal findings on laboratory evaluations, regardless of severity, will be followed by SIs until satisfactory resolution.

### 13.10.1 Pregnancy

A subject's reported pregnancy at any time during study participation starting after the first dose of study drug through the final study visit is considered an AE and must be reported to NIDA in accordance with the reporting requirements described in **Appendix I**. Subjects who become pregnant will be discontinued from the study drug and will be referred for appropriate treatment as necessary. Subjects will be asked to sign a release of information form for study personnel to access medical records to obtain information regarding the outcome of the pregnancy.

### 13.11 Serious Adverse Events

Each AE or reaction will be classified by the SI as serious or non-serious. Based on the seriousness of the adverse event or reaction, appropriate reporting procedures will be followed. The "*International Conference on Harmonisation (ICH) Guideline for Industry: Clinical Safety Data Management: Definitions and Standards for Expedited Reporting, ICH-E2A March 1995*," as implemented by the U.S. Food and Drug Administration defines serious adverse event (SAE) or reaction as any untoward medical occurrence that at any dose:

- results in death;
- is life-threatening; (*NOTE: The term "life-threatening" in the definition of "serious" refers to an event in which the patient was at risk of death at the time of the event; it does not refer to an event which hypothetically might have caused death if it were more severe.*)
- requires inpatient hospitalization or prolongation of existing hospitalization;
- results in persistent or significant disability/incapacity; or
- is a congenital anomaly/birth defect.

In addition, important medical events that may not result in death, be life-threatening, or require hospitalization may be considered a serious adverse drug reaction, when based on appropriate medical judgment that may jeopardize the subject and may require medical or surgical intervention to prevent one of the outcomes listed in the above definition. An unexpected event is one that is not described with respect to nature, severity, or frequency in the current Investigator's Brochure or product package insert.

Reporting of AEs and SAEs is described in **Appendix I**. There can be serious consequences including criminal and/or civil penalties for Sponsors who fail to comply with FDA regulations governing the reporting of SAEs to FDA. The SIs in this study have the responsibility of promptly reporting all SAEs to NIDA in order that NIDA, as the IND Sponsor, can comply with these regulations.

If a study subject withdraws from the study or if a SI decides to discontinue the subject from the study because of a SAE, the subject must have appropriate follow-up medical monitoring. If the subject is hospitalized, medical monitoring will consist of not less than daily evaluation by physical examination, vital signs, laboratory evaluations, and if applicable, ECG monitoring for significant treatment-emergent abnormalities. Monitoring will continue until the problem prompting hospitalization has resolved or stabilized with no further change expected or is discovered to be clearly unrelated to use of investigational products or progresses to death.

### **13.12 Subject Confidentiality**

To maintain subject confidentiality, all laboratory specimens, eCRFs, and reports will be identified by an alpha-numeric code. Clinical records will be stored separately from research records in a secure location. Subject information will not be released without the subject's written permission, except as necessary for monitoring by the FDA, the VA CSP, and Sponsor authorized monitors. Release of personal health information will be in accordance with current Standards for Privacy of Individually Identifiable Health Information (45 CFR parts 160 and 164) of the Health Insurance Portability and Accountability Act (HIPAA).

Particular attention is drawn to the regulations promulgated by the FDA under the Freedom of Information Act providing, in part, that proprietary information furnished to SIs and IRBs will be kept confidential by the FDA only if maintained in confidence by the SI and IRB.

By participating in this protocol the SI affirms to NIDA that information furnished to the SI by NIDA will be maintained in confidence and such information will be divulged to the IRB, Ethical Review Committee or similar expert committee; affiliated institution; and employees only under an appropriate understanding of confidentiality with such board or committee, affiliated institution and employees.

By participating in this protocol the SI agrees that within local regulatory restrictions and ethical considerations, NIDA or any regulatory agency may consult and/or copy study documents in order to verify eCRF data.

The procedure for applying for a certificate of confidentiality is provided in **Appendix II**.

## **14 STATISTICAL ANALYSIS**

Descriptive statistics will be used to present study data. Continuous variables will be presented as number of observations (n), mean, standard deviation (SD), median, minimum and maximum values. Categorical variables will be presented as counts and percentages. All data will be presented separately by treatment group. Summaries of the safety data will be presented for the Safety Population and the Evaluable Population. All data will be presented in listings.

## 14.1 Predictive Enrichment Strategy and Sample Size

A predictive enrichment strategy based on pre-randomization data (collected during screening and the one-week, single-blind run-in period) will be used to define a subpopulation of study participants who are likely to be medication adherent after randomization and likely to exhibit a low placebo response rate. Data from only this subpopulation, termed the “prequalified for primary efficacy endpoint” (PPEE) population, will be utilized for the primary efficacy endpoint. Predictive enrichment strategies have been endorsed by the FDA (US Department of Health and Human Services Food and Drug Administration. Guidance for industry enrichment strategies for clinical trials to support approval of human drugs and biological products, December, 2012) and their use has been suggested as a means to address the overlapping issues of medication nonadherence, “professional subjects” and increasing placebo response rates (McCann *et al.*, 2015).

While 272 subjects will be enrolled in the current study, it is estimated that 180 subjects (approximately 90 subjects per group) will meet criteria for inclusion in the PPEE population. Assuming 6% and 20% success rates (for achieving abstinence from cocaine) during placebo and lorcaserin treatment, respectively, 90 subjects per group in the PPEE population would yield 80% power (Pearson’s Chi-square test for two proportions; two-sided comparison, alpha = 0.05). The assumption of 6% success in the placebo group is based on results from similar cocaine medication trials conducted by NIDA in the past, using the same definition of “success” (placebo group success rates have ranged from 0 to 9%). The goal of 20% success in the lorcaserin group would constitute slightly more than a three-fold increase in success compared to the expected placebo success rate. Such efficacy would be clinically meaningful. No medications are currently approved for the treatment of cocaine use disorder, but a 3-fold increase in quit rate (vs. placebo) would constitute greater efficacy than has been observed for FDA-approved smoking cessation medications. A recent meta-analysis of randomized, placebo-controlled smoking cessation trials (Eisenberg *et al.*, 2008) revealed that placebo and bupropion quit rates were 11% and 20%, respectively (16 trials), placebo and nicotine gum quit rates were 14% and 19%, respectively (22 trials), placebo and nicotine patch quit rates were 7.5% and 13%, respectively (30 trials), and placebo and varenicline quit rates were 15% and 26%, respectively (13 trials). For the current study, multiple factors were considered in estimating that 180 of the 272 enrolled subjects will qualify for inclusion in the PPEE population. Further explanation requires an understanding of enrichment strategy details.

For a subject to be included in the PPEE population, two criteria must be met. First, the plasma sample collected prior to randomization on Study Day 8 must yield an acetazolamide concentration of at least 15 ng/mL. Based on a prior NIDA PK study (unpublished), plasma acetazolamide concentrations can be expected to stay above 15 ng/mL for 48 hours after a single 15 mg oral dose in approximately 99.9% of subjects (the lower boundary of the 99.9% CI for plasma samples collected 48 hours post-dose was 15.2 ng/mL). As subjects are supposed to take 15 mg acetazolamide capsules twice daily during the single-blind run-in period (with the last dose on the morning of Study Day 8), they would have to miss at least three or more consecutive doses at the end of the run-in period for their plasma concentrations to fall below 15 ng/mL during the clinic visit on Study Day 8. When such extreme nonadherence occurs during the first week of a trial, it brings into question the motivation of the subject. Such a subject may not be interested in receiving treatment and may have falsely claimed to be “treatment seeking” to gain

study enrollment. Unfortunately, deception to gain enrollment has been well-documented in repeat clinical trial participants (Devine *et al.*, 2013; Shiovitz *et al.*, 2013). In a prior NIDA trial that evaluated modafinil in the treatment of methamphetamine dependence (Anderson *et al.*, 2012), 10% of subjects in the active treatment groups never had any detectable modafinil in their urine samples from week 1 through the end of the 12-week trial. Based on this experience, it is estimated that approximately 10% of subjects who enroll in the current study will fail to meet the 15 ng/mL acetazolamide cutoff level and will therefore not qualify for the PPEE population.

The second criterion for inclusion in the PPEE population is focused on cocaine use self-report data collected during the first day of screening. To be included in the PPEE population, subjects must report using cocaine on at least 8 days during the 30 days immediately prior to screening. Subjects reporting 1 to 7 days of cocaine use will still be enrolled, and their data will be evaluated for exploratory efficacy endpoints, but they will not qualify for the PPEE population. In an unpublished evaluation of recent NIDA-sponsored cocaine medication trials, higher placebo success rates were observed for subjects reporting <8/30 days of cocaine use immediately prior to screening. For example, in a trial evaluating nopicastat vs. cocaine dependence (manuscript in preparation), 18% of placebo subjects reporting <8/30 days of cocaine use prior to screening were successful in achieving 3 weeks of abstinence at the end of the study, whereas only 6% of placebo subjects reporting >7/30 days of cocaine use prior to screening were able to achieve this same duration of abstinence. In the nopicastat trial, 22% of enrolled subjects reported <8/30 days of cocaine use. Based on this experience, we estimate that approximately 22% of subjects who enroll in the current trial will report <8/30 days of cocaine use prior to screening and, therefore, will not qualify for the PPEE population.

In addition to subjects failing to meet the two criteria mentioned above, it is anticipated on the basis of past experience that approximately 5% of subjects who are enrolled in the current study will drop out prior to randomization on Study Day 8 (a 5% dropout rate was seen during the first week of the NIDA nopicastat trial).

[figure not shown]
With the above factors in mind, the estimated size of the PPEE population can be addressed. If 272 subjects are enrolled and 22% (60) report <8/30 days cocaine use (excluding them from the PPEE population), 212 subjects remain eligible. If approximately 10% (22) of the remaining 212 subjects fail to qualify for the PPEE population based on nonadherence during the run-in period (Study Day 8 plasma acetazolamide <15 ng/mL), 190 subjects remain eligible. If approximately 5% (10) of the remaining 190 subjects drop out prior to Study Day 8, 180 subjects will qualify for the PPEE population.

While the enrichment strategy adds complexity to the process of data analysis, it does not substantively complicate clinical site procedures. Subjects will be classified as “PPEE” or “Non-PPEE” during data analysis, and clinical site staff will not be aware of key data (acetazolamide plasma concentrations) required for the classification.

**Figure 3** schematically depicts this predictive enrichment strategy for the purposes of endpoint analysis.

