**EFFICACY ASSESSMENTS:** An enrichment strategy based on pre-randomization data from the run-in phase will be used to define a subpopulation of study participants who are likely to be medication adherent during the Treatment Phase and who are likely to exhibit a low placebo response rate. Data from only this subpopulation, termed the “prequalified for primary efficacy endpoint” (PPEE) population, will be utilized for the primary endpoint success/failure analysis. The PPEE population consists of subjects who have demonstrated adherence to the acetazolamide run-in regimen (based on the plasma sample collected on Study Day 8) and who, on the first day of Screening, reported 8 or more days of cocaine use in the previous 30 days. The primary endpoint is the percentage of subjects successfully achieving abstinence from cocaine during the last three weeks of treatment (Study Weeks 11-13) in the PPEE population.

At the beginning of Study Day 1, at each weekly clinic visit from Week 1 through Week 14, and at the Week 16 Follow-Up Visit, data for the efficacy endpoints will be collected (including urine BE, cotinine and alcohol).

A subject will be regarded as a treatment success (abstinent from cocaine during the last three weeks of treatment) if:

- a. There are self-report data indicating no cocaine use on each day of the 3-week period;
- b. There is at least one benzoylecgonine (BE) assay result for a urine sample collected within the 3-week period; and
- c. BE assay results are negative (BE <150 ng/mL) for all urine samples collected during the 3-week period.

Subjects not meeting these three criteria (including dropouts) will be regarded as treatment failures.

The secondary endpoint is the proportion of subjects who successfully achieve abstinence from cocaine during the last three weeks of treatment (Study Weeks 11-13) in the subset of the PPEE population who are either Non-Drinkers or who are attempting alcohol abstinence, as evidenced by their decision to continue viewing the alcohol intervention modules on Study Day 8. Comparison of this proportion in subjects receiving lorcaserin vs. placebo will constitute the secondary endpoint analysis. In the analysis, abstinence will be defined as described for the primary endpoint.

An important exploratory endpoint will focus on the efficacy of lorcaserin in facilitation of abstinence from alcohol based on self-reported drinking and urine ethyl glucuronide (EtG) assays.

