**NOTE: The last day of screening cannot be the first day of enrollment**

## 11.3 Scheduling of Study Day 1 Visit

As soon as possible after a subject has passed all screening assessments, s/he should be contacted to schedule both the Study Day 1 visit and the Study Day 8 visit. Subjects must be available on the same day of the week for two consecutive weeks to accommodate this scheduling because missing the Study Day 8 visit results in early termination from the study. The Study Day 1 visit should be scheduled as soon as possible and no later than 21 days after signing the consent form.

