### **14.3 Outcome Measures**

#### **14.3.1 Primary Efficacy Outcome Measures**

The primary endpoint is the proportion of subjects successfully achieving abstinence from cocaine during the last three weeks of treatment (Study Weeks 11-13) in the PPEE population. Comparison of this proportion in subjects receiving lorcaserin vs. placebo will constitute the primary endpoint analysis.

A subject will be regarded as a treatment success (abstinent from cocaine during the last three weeks of treatment) if:

- There are self-report data indicating no cocaine use on each day of the 3-week period;
- There is at least one benzoylecgonine (BE) assay result for a urine sample collected within the 3-week period; and

- BE assay results are negative (BE <150 ng/mL) for all urine samples collected during the 3-week period.

Subjects not meeting these three criteria (including dropouts) will be regarded as treatment failures.

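### Day 1 and Day 8 urine BE are collected but not used in the primary comparison; stratifying on Day 8 BE would add modest precision and guard against chance imbalance

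*Combined protocol and SAP*

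**What the plan says.** **Enrichment criterion.** Section 14.1 defines PPEE by a Day 8 plasma acetazolamide cutoff and by cocaine use: "subjects must report using cocaine on at least 8 days during the 30 days immediately prior to screening". The report is taken on the first day of screening.

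**Timing.** Screening begins at consent (Section 11.2). Day 1 must come "no later than 21 days after signing the consent form" (Section 11.3). Randomisation is on Day 8, after a one-week run-in (Section 7). Individual CBT is offered from Week 1 (Section 10.2), so at least one session can precede randomisation.

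**BE before randomisation.** Exclusion 5 in Section 8.3 requires one BE-positive urine at any point in screening. The Synopsis schedules efficacy data, including urine BE, "At the beginning of Study Day 1, at each weekly clinic visit from Week 1 through Week 14". Table 3 marks BE at Day 1 and Day 8, and Section 12.20 sends it to a central laboratory for quantitative assay.

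**Endpoint and test.** Section 14.3.1 states: "The primary endpoint is the proportion of subjects successfully achieving abstinence from cocaine during the last three weeks of treatment". Success depends only on Weeks 11-13. The comparison is of two proportions, with no covariate named. The only test named is the Pearson chi-square in the sample-size text ("two-sided comparison, alpha = 0.05").

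**Where BE does not appear.** Pre-randomisation BE is absent from the PPEE criteria, the three stratification factors (Section 7), the ten populations (Section 14.2) and the listed outcomes (Section 14.3). By contrast, urine EtG through Day 8 helps define Non-Drinkers, and the Day 1 and Day 8 craving scores form the BSCS baseline.

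**The concern.** The enrichment strategy is meant to select subjects with a low placebo response, on the premise that baseline cocaine use predicts placebo success. The cocaine information used for this is the oldest available. The most recent, an assay of the endpoint's own biomarker on the day of randomisation, is not used. A subject who reported 8 or more use days but is BE-negative on Day 1 and Day 8 still belongs to PPEE. If that state lasts through Weeks 11-13, with matching self-report, the subject counts as a success.

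The one stratification factor on cocaine use is the same <8 versus 8-or-more split that defines PPEE. Within PPEE it takes a single value, so it balances nothing there.

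At stake are precision, protection against chance imbalance in a small-event comparison, and the meaning of the result: whether the drug helps subjects stop or helps those who have recently stopped stay stopped.

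**Working it through.** **1. Age of the self-report at randomisation.** 21 days (longest consent-to-Day 1 interval) + 7 days (run-in) = 28 days. This is a maximum, because Section 11.3 asks for Day 1 as soon as possible.

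**2. The plan's power.** Section 14.1 gives the inputs: "Assuming 6% and 20% success rates (for achieving abstinence from cocaine) during placebo and lorcaserin treatment, respectively", and "90 subjects per group in the PPEE population would yield 80% power". With p0 = 0.06, p1 = 0.20, mean 0.13 and n = 90:

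z = [0.14 × √90 − 1.96 × √(2 × 0.13 × 0.87)] / √(0.06 × 0.94 + 0.20 × 0.80) = (1.328 − 0.932) / 0.465 = 0.851

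Power = Φ(0.851) = 80.3%, so the stated figure reproduces. The exact power of the uncorrected chi-square is 82.3%. Expected successes are 90 × 0.06 = 5.4 and 90 × 0.20 = 18, a gap of 12.6.

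**3. An anchor for prognostic strength.** The only gradient in the documents is in Section 14.1: 18% placebo success with <8/30 use days against 6% with more. The odds ratio is (0.18/0.82) / (0.06/0.94) = 3.4. It belongs to a different predictor (self-reported use days), so it is only a rough guide.

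**4. Average gain from stratifying.** Assumptions: a share of 10%, 20% or 30% BE-negative on Day 8; an odds ratio (OR) for success, BE-negative versus BE-positive, of 3.4, 4, 8 or 15; and the same treatment odds ratio in both strata. The model is logit P(success) = a(arm) + ln(OR) × BE-negative, with a(arm) solved so that overall success stays at 6% and 20%. Trials of 90 per arm were simulated (200,000 per scenario), with both tests at |z| > 1.96.

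| OR (assumed) | Unadjusted chi-square | Mantel-Haenszel, share 10-30% |
|---|---|---|
| 3.4 | about 82% | 82.8-83.4% |
| 4 | about 82% | 83.0-83.8% |
| 8 | about 82% | 85.2-86.2% |
| 15 | about 82% | 88.1-89.3% |

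Under the null, type I error is about 4.3-4.4% unadjusted and 4.7-4.9% stratified, so both tests are valid. Part of the small gain at low odds ratios reflects the slight conservatism of the unadjusted test.

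**5. When the arms are imbalanced.** An imbalance of 5 or more BE-negative subjects, in either direction, occurs in about 26%, 40% and 46% of trials at shares of 10%, 20% and 30%. In trials where lorcaserin has at least 5 fewer, power at OR 4 is about 74% unadjusted and 82-84% stratified. This is one tail; the averages in step 4 already include both.

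**6. How far an imbalance moves the result.** At a 20% share and OR 4, the success rates (BE-positive, BE-negative) are 4.0% and 14.2% on placebo, and 14.8% and 40.9% on lorcaserin. Five subjects shift the gap by about 5 × (0.102 + 0.261)/2 = 0.9 success. Over the range of shares this is 0.8-1.0 at OR 4 and 1.5-2.2 at OR 15, against the expected gap of 12.6.

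**7. If lorcaserin does nothing for subjects already BE-negative.** Here 6% and 20% are assumed to apply only to the others, and BE-negative subjects succeed at the same assumed rate in both arms. With that rate at 30%, stratifying moves power from 68% to 69% (share 10%) and from 53% to 55% (share 20%). With it at 50%, the moves are 63% to 68% and 46% to 52%.

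**The case against.** The plan works as designed without this change. Randomisation protects the comparison, the chi-square holds its level, and unadjusted power is already above target. The nominal alpha allows for chance imbalance. At the only odds ratio that the documents suggest, 3.4, the average gain is about half a point to one point; nothing in them supports 8 or 15. All of this stands, and it limits the weight of the point.

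Four stronger readings are tempting, and the documents do not support them:

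- **That the result is biased or its error rate inflated.** BE status precedes randomisation, and step 4 shows no inflation.
- **That an imbalance could by itself create or hide the effect.** Step 6 puts the shift from five subjects at one to two successes out of 12.6.
- **That the trial is underpowered.** The low figures in step 7 need 6% and 20% to apply only to subjects still using. Section 14.1 takes the 6% from earlier trials with the same success definition, so it may already include early abstainers.
- **That BE-negative subjects on Day 8 are already abstinent.** The plan's own definition needs daily self-report and negative BE over three weeks. One negative sample is not that, and the documents give no BE detection window.

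Section 14 also defers some details to a Statistical Analysis Plan, and no separate text is among the documents. It might add an adjustment. Sections 14.1 and 14.3.1 name none for the primary comparison, so the gain over the one test named remains.

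**Conclusion.** The point holds as a missed, nearly free improvement, not as a threat to validity. The enrichment self-report can be 28 days old at randomisation, the BE results from the run-in are unused, and no stratification factor carries cocaine-use information within PPEE.

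On average the loss is small at the documents' own gradient and reaches about 6 points only under a strong assumed relation. The clearer benefits are protection in trials that happen to be imbalanced and a result that can be described by BE status at randomisation. These sizes rest on an assumed BE-negative share of 10-30%, assumed odds ratios and a common treatment odds ratio. If the drug has no effect in BE-negative subjects, the gain is 1-2 points at 30% success among them and 5-6 points at 50%.

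**What to change.** Keep the PPEE definition and the sample size. Before unblinding, prespecify in Section 14.3.1 and the SAP that:

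- the primary PPEE comparison is a Mantel-Haenszel test stratified by one factor, Day 8 BE (<150 versus ≥150 ng/mL);
- Day 1 BE is used where the Day 8 result is missing;
- success is reported by arm within each stratum, descriptively only, because numbers will be small (a 20% share would be 18 subjects per arm);
- the unadjusted chi-square is given as a sensitivity analysis.

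The cost is analysis wording. The samples are already scheduled, and strata can be assigned at analysis, as PPEE status already is, so no site procedure changes. The downside is slightly more complex reporting and a headline test that is no longer the plain chi-square used for the sample size.
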